As this is the first study to examine homebased exercise snacking in outpatients identified as at risk of falling, it is crucial to assess the acceptability of the exercise snacking. As evidenced by Rasinaho, Hirvensalo [19], often adherence to an exercise intervention is accompanied by other more subtle changes in everyday behaviours, such as further changes to non-exercise physical activity patterns. However, there are inevitably challenges to adherence associated with home based exercise that have the potential to undermine the effectiveness of an exercise programme [20]. As such, a qualitative approach lends itself to assessment of subjective ratings of the exercise snacking regime.

3. Aims

The primary aim of this pilot study is to explore the acceptability of a 28-day homebased exercise snacking intervention to improve leg strength in older adults who have attended the memory clinic at the RICE Centre in Bath. The secondary aim is to examine the influence of exercise snacking on measures of physical function relevant to this population and the feasibility of collecting these data.

4. Study Design

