4.1 Research Design

This is a single cohort acceptability study. All participants will receive the intervention, and pre- and post-testing.

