4.4.2 Screening

All potential participants will undergo a face-to-face screening meeting with a member of the research team at the RICE Centre, to assess eligibility based on criteria described in Section 5 before proceeding. If the participant has a carer, then they may also attend the session. Potential participants will be asked to wear clothes in which it is comfortable to complete simple movement tasks. Before commencing any assessment, the screening and study procedures will be verbally described to the potential participant by the researcher, and they will be given the opportunity to ask questions about the study. If the potential participant is happy to continue with the screening and the study, subject to meeting eligibility criteria, they will be asked to sign an informed consent form.

A stadiometer and balance scales will be used to determine the potential participant's height and weight for calculation of Body Mass Index (BMI). Potential participants will complete a bespoke health screening questionnaire based on study exclusion criteria, and mini-mental state examination (MMSE) [21]. Those identified as meeting any exclusion criteria or with an MMSE score of <20 will be excluded from the study at that point.

Potential participants will then undertake an objective assessment of physical function (Short Physical Performance Battery; SPPB [22]) in which simple tests of walking speed, ability to repeatedly rise from a chair, and simple standing balance are scored based on set criteria. Only participants scoring over three and no more than eight out of twelve, without scoring zero on any element of the test will be eligible to continue the

screening. The upper limit to the SPPB eligibility criteria is to deliberately target a cohort who demonstrate some degree of compromised strength and balance.

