Participants will receive a thorough demonstration of the exercise snacking movements. They will be asked to demonstrate their ability to safely carry out the movement themselves to the satisfaction of the researcher, who may then provide further guidance and opportunity for the participant to practice the movements if required. If the participant is unable to safely complete the exercises without loss of balance or experiencing acute joint pain whilst performing the movements, or the participant, their carer, or researcher feels that the participant would be placed in undue risk by undertaking exercise snacking in the home unsupervised, then they will be excluded from the study.

Eligible participants who successfully pass the aforementioned screening tests will be invited to continue in the study, and those wishing to do so will then undertake the baseline assessment during the same visit.

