4.4.3 Baseline assessment

Baseline questionnaires and cognitive tests will be completed (paper form). The questionnaires will include brief measures of attitudes- (Outcome Expectancy for Exercise Questionnaire), self-confidence- (barrier self-efficacy scale), and psychological need satisfaction- (PNSE) for exercise, and a series of questionnaires designed to evaluate current mental health (Patient Health Questionnaire, Generalised Anxiety Disorder Assessment and Subjective Vitality Index), General Health (Short Form Health Survey) and Quality of Life (Life Satisfaction Scale, Global Quality of Life Scale). Measures of health and wellbeing will include a researcher led cognitive test (Montreal Cognitive Assessment), the Gronigen Frailty Indicator (GFI) [23].

As a collective measure of physical function, the SPPB score from the screening will be used, with the additional assessment of physical function described herein only undertaken with participants that have passed the screening and chosen to enrol in the study

Lower limb functional capacity will be assessed by a 60-second sit-to-stand test (STS-60) from a standardised, firm seated chair. For this assessment, as many sit-to-stand repetitions as possible will be completed, with the participant initially sitting fully on the chair, and rising to a full standing height with knees extended, without the use of arms for assistance with movement. Arm movement to maintain balance will be permitted, however the participant will be encouraged to minimise use of the arms to push off from the chair during the movement, rather the legs should initiate the movement. Whilst timing and counting the number repetitions performed, the researcher will be at all times vigilant to any potential loss of balance, and will stop the test if they feel the participant is unduly stressed or at risk of falling. The chair seat height will be 45 cm (the height of a standard kitchen chair). Participants will not be able to see the time remaining on the test, and no verbal encouragement will be provided. Immediately after completing the STS-60, participants will be asked to provide a rating of perceived exertion for the test using the 7-20 Borg scale [24].

As a measure of static standing balance, participants will be asked to complete simple tests of standing balance lasting a maximum of 60 seconds. Tests will consist of feet in

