4.4.4 Follow-up assessment

Follow-up assessment will take place within 5 days of the final day of the 28-day intervention. The follow-up assessment is planned to take place at the RICE Centre. However, due to the uncertainty of the ongoing COVID-19 pandemic, there is the possibility of future lockdowns being implemented, or the participant being required to self-isolate whilst enrolled in the study. As the exercise snacking intervention is deliberately intended to be performed in the home the intervention should be able to continue uninterrupted, provided that the participant will not be alone when performing the exercise bouts. In the event that participants are not able to attend the testing facility for follow up assessment, this may be conducted remotely using video calling. This approach was successfully implemented in a recent study conducted whilst older adults were following government guidance to 'shield' during March to June 2020 [26]. However, in the aforementioned study, older adults without physical access to the information and communications technology (ICT) capable of video calling or lacking the digital literacy to use video calling software, were not able to take part in the study. To address this in the present study, tablets with pre-paid sim card/wifi dongles will be provided, along with written instructions for use of a GDPR compliant video calling software. The questionnaire-based assessments will still be completed on paper forms during the follow-up assessment video call, and they will be delivered with the tablet.

Questionnaires will be completed in the same order as the baseline assessment, but preceded by an additional questionnaire based on the theoretical framework of acceptability (TFA), which contains 8 items measuring general acceptability and the 7 distinct components of the framework [27] to assess acceptability of the exercise snacking intervention. Participants will repeat the same tests of physical function as completed in the baseline assessment (including the SPPB previously completed in the screening), under the same conditions as previously.

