To complete the physical function tests remotely participants must be accompanied at all times by someone else (e.g. carer or another member of the household). Researchers will instruct the participant on where to place the tablet and chair for the SPPB chair test and STS-60 for a view that allows the test to be carried out as in the baseline assessment. For the balance measures of the SPPB and static standing balance measures, the participant will be reminded that they can position a stable item nearby in case they feel at risk of losing balance. The 2.4 m walk element of the SPPB and the TUG will be omitted in cases where the follow-up testing is completed remotely.

Qualitative assessment of experience of the protocols: Following the intervention participants will be invited to take part in an interview to provide qualitative feedback on their experience of the intervention. Interviews will take place in person or via video calling accordingly, will be digitally recorded, transcribed verbatim and anonymized on completion. The interview schedule will cover; (i) participants' perceptions of the impact of exercise snacking on mood, appetite, vitality, sleep, and other participant-generated concerns, (ii) adherence to the study protocol, i.e., if and how participants adapted the prescribed regimes, and factors they suggest would make the protocol easier to adopt, and (iii) the perceived barriers and facilitators, and costs and benefits of exercise-snacking. Transcripts will be analysed systematically using framework analysis to highlight key themes within and across participants, and the results used to facilitate participant input into the feasibility analysis and protocol amendments.

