5.1 Inclusion Criteria

In order to participate in this study, volunteers must satisfy all of the following criteria:

- Aged >65 years
- Have attended the Memory Clinic at the RICE Centre in Bath
- Mini-mental state examination (MMSE) score of ≥ 20 [21]
- Short Physical Performance Battery (SPPB) [22] score 3-8 and not scoring 0 on any component of the test
- Capability to safely perform the exercise snacking movements, assessed by a researcher during screening, and be able to have someone present in the home who could call for help if required during all exercise snacks.
- Not regularly engaging in recreational sports or structured exercise (once a week or more).
- Have a foreseeable clear period of 28 consecutive days in which to perform the exercise snacking protocol (i.e. no planned holidays or hospitalisation)

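### The SPPB score that decides entry is also the baseline for a pre-post t-test in a single cohort, so SPPB change may carry a regression-to-the-mean drift that the plan does not address (minor)

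*Combined protocol and SAP*

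**What the plan says.** - **Entry.** Section 4.4.2 admits "Only participants scoring over three and no more than eight out of twelve, without scoring zero on any element of the test". Section 5.1 gives the criterion as "score 3-8 and not scoring 0 on any component of the test". Section 4.4.2 adds that the upper limit is there on purpose, to recruit people with some loss of strength and balance.
- **A further exclusion at the same visit.** After the SPPB, section 4.4.2 excludes people who lose balance or have acute joint pain when trying the exercises, or who are judged to be at undue risk. Of the rest, "those wishing to do so will then undertake the baseline assessment during the same visit".
- **Baseline.** Section 4.4.3: "As a collective measure of physical function, the SPPB score from the screening will be used". No second SPPB is planned before the intervention.
- **Follow-up.** Section 4.4.4 repeats the function tests once, "including the SPPB previously completed in the screening". For remote visits: "The 2.4 m walk element of the SPPB and the TUG will be omitted in cases where the follow-up testing is completed remotely".
- **Design and aim.** Section 4.1: "This is a single cohort acceptability study". The secondary aim in section 3 is to "examine the influence of exercise snacking on measures of physical function relevant to this population and the feasibility of collecting these data".
- **Analysis.** Section 4.5 (Data Analyses) lists SPPB among the secondary outcomes and applies Student's t-test to pre-to-post change at P < 0.05. Acceptability, the primary outcome, is assessed qualitatively and descriptively.

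No section mentions regression to the mean, an adjustment for it, or a caution on reading SPPB change.

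**The concern.** The t-test takes zero mean change as its null. When people are admitted because an error-prone score fell inside a window, and that same score is the baseline, the expected change is generally not zero even if no one's true function alters. The follow-up mean moves towards the mean of all those screened. A larger sample would not remove this, and no control group would reveal it.

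Uncontrolled pre-post change never isolates an exercise effect, and that limit applies to every secondary outcome here. SPPB has an additional problem: among the outcomes in section 4.5 it is the only one whose baseline is itself an entry score. MMSE also decides entry but is not an outcome. STS-60, TUG and the 60-second balance tests come after the SPPB has been passed.

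At stake is the reading of one secondary P value. A significant gain could partly reflect selection, or a real gain could be partly masked if the drift is downward.

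**Working it through.** **Inputs from the documents.** Window 4 to 8 (section 4.4.2) or 3 to 8 (section 5.1), with no element scored zero; 20 completers (section 4.3); alpha 0.05 (section 4.5). The figure of 20 is a judgement with no effect size, SD or power behind it, so there is no calculation to reproduce.

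**Assumptions not in the documents.** Three elements scored 0 to 4, correlated 0.5; total SD 2.5 to 3; retest ICC 0.75 to 0.90; no true change; paired two-sided test. The mean of those screened is varied.

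**Step 1, the mechanism by hand.** For a normal score, drift = (1 - ICC) x (screened mean - mean first score of those admitted). Take mean 7, SD 2.5, ICC 0.80 and window 4 to 8, with limits 3.5 and 8.5 before rounding:
- Standardised limits: (3.5 - 7)/2.5 = -1.4 and (8.5 - 7)/2.5 = 0.6.
- Share admitted: 0.726 - 0.081 = 0.645.
- Mean of those admitted: 7 + 2.5 x (0.150 - 0.333)/0.645 = 6.29.
- Drift: 0.20 x (7 - 6.29) = +0.14. Simulation of the same total-score model gives +0.15.

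**Step 2, effect on the test.** With a change SD of 1.57 (from that simulation) and n = 20, the noncentrality is 0.15/(1.57/√20) = 0.43. The chance of a false significant improvement is then about 6%, against a nominal 2.5%.

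**Step 3, the rule with no zero element.** Three rounded elements per person, totals 4 to 8, second score drawn from the same true values, 2,000,000 people per setting. Ranges are over SD and ICC.

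| Screened mean | Drift (points) | False improvement (nominal 2.5%) | False result in either direction (nominal 5%) |
|---|---|---|---|
| 5 | -0.11 to -0.25 | 0.6 to 1.1% | about 6.4 to 8.3% |
| 6 | -0.01 to -0.04 | 2.2 to 2.4% | about 5.0 to 5.2% |
| 7 | +0.08 to +0.18 | 4.3 to 6.4% | about 5.6 to 7.1% |
| 8 | +0.18 to +0.38 | 7.7 to 15.1% | not tabulated |
| 9 | +0.28 to +0.59 | 13 to 30% | not tabulated |

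Drift crosses zero at a screened mean of about 6.1 to 6.2. At mean 5 the likelier error is a false decline, at about 5 to 8%. Mean 9 is an extreme case: only 38 to 40% of those tested would be admitted. A total-score model over a wider grid (means 4 to 10, SD 2 to 3, reliability 0.7 to 0.9, either window) spans about -0.48 to +0.99. That spread shows how far the answer depends on the assumptions.

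**Step 4, the lower limit.** With elements scored 1 to 4, the number of patterns giving totals 4, 5, 6, 7 and 8 is 3 + 6 + 10 + 12 + 12 = 43. A total of 3 adds one pattern, 1+1+1, making 44. The two sections differ for that pattern only.

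**Step 5, remote follow-up.** Anyone admitted scored 1 to 4 on the walk. If a remote total were summed without it, that total would be 1 to 4 points lower with no real change. If 2 of 20 were remote (illustrative), the mean change would be lower by 2/20 x (1 to 4) = 0.1 to 0.4 points. If the total were treated as missing there would be no such shift, but those people would drop out of the comparison. No rule says which applies.

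**The case against.** **The drift may be negligible.** This stands. Near a screened mean of 6 it is almost zero, and between 5.5 (-0.06 to -0.14) and 7 it stays below 0.2 points. The figures illustrate a mechanism and do not estimate anything for this trial. Recruitment is filtered by gerontologist judgement and a phone check (section 7), and section 2 describes the target patients as at risk of falling. Both make a high screened mean less likely, but neither fixes the mean.

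**The simulation leaves out a selection step.** This also stands. The exercise-safety exclusion comes after the SPPB at the same visit. If same-day performance affects both, it favours people having a good day and may add a downward component that the table does not contain.

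**Removing one P value is partly preference.** Other uncontrolled outcomes keep theirs, and SPPB is one of many secondary measures in a pilot that claims no sample-size basis for function. This is a fair argument for a low rating. A stated limitation with the screening data would be the minimum. SPPB still differs, because its expected change under no effect is generally not zero.

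**Stronger readings that the documents do not support.** A reader might infer that SPPB gains will be inflated. The window cuts at both ends, so the sign depends on a mean that is not given. A reader might also infer that STS-60 is the safer measure to rely on. Section 4.5 (Exercise snacking intervention) has participants do one minute of sit-to-stand twice daily, nearly the same task, so practice effects apply. Nor do the two lower limits explain the drift, since they differ by one pattern. The remote-visit gap does not touch on-site follow-ups, which are what is planned.

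**Conclusion.** The concern holds as a minor point. SPPB change may carry a selection drift because its baseline is the entry score, and the plan neither adjusts for this nor warns of it. Size and sign cannot be fixed from the documents. Over screened means of 5 to 7 the modelled drift is at most about a quarter of a point either way, with modest distortion of the error rate. It becomes substantial only at means of 8 to 9. All of this rests on the assumed SD, reliability and element structure, and omits the exercise-safety exclusion.

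Two separate points rest on the text alone. Sections 4.4.2 and 5.1 disagree on whether a total of 3 is eligible. If a follow-up is remote, its SPPB total is not comparable with the screening total. The primary acceptability aim is not affected by the drift.

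**What to change.** 1. In section 4.5 (Data Analyses), report SPPB change descriptively with its confidence interval and no significance test. State that the baseline is the selection score, so neither the mean change nor its interval can be read as an exercise effect. The statement must cover the interval, since an interval excluding zero would otherwise be read as a test.
2. Report the SPPB mean and SD of everyone who takes it at screening, with the numbers excluded above the window, below it and at the exercise-safety step. Readers can then judge the likely direction of drift. Consent is signed before screening (section 8); check that it covers this use for people then excluded.
3. If any follow-up is remote, compare the balance plus chair-stand sub-score at both visits for everyone, and the full total for in-person follow-ups only. This removes the scale mismatch but not the selection drift.
4. Reconcile the SPPB lower limit between sections 4.4.2 and 5.1.

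The cost is wording plus a summary of scores already collected, with no new visits, tests or staff. SPPB loses its P value, and the sub-score is less familiar than the total.

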4.4.4 Follow-up assessment

Follow-up assessment will take place within 5 days of the final day of the 28-day intervention. The follow-up assessment is planned to take place at the RICE Centre. However, due to the uncertainty of the ongoing COVID-19 pandemic, there is the possibility of future lockdowns being implemented, or the participant being required to self-isolate whilst enrolled in the study. As the exercise snacking intervention is deliberately intended to be performed in the home the intervention should be able to continue uninterrupted, provided that the participant will not be alone when performing the exercise bouts. In the event that participants are not able to attend the testing facility for follow up assessment, this may be conducted remotely using video calling. This approach was successfully implemented in a recent study conducted whilst older adults were following government guidance to 'shield' during March to June 2020 [26]. However, in the aforementioned study, older adults without physical access to the information and communications technology (ICT) capable of video calling or lacking the digital literacy to use video calling software, were not able to take part in the study. To address this in the present study, tablets with pre-paid sim card/wifi dongles will be provided, along with written instructions for use of a GDPR compliant video calling software. The questionnaire-based assessments will still be completed on paper forms during the follow-up assessment video call, and they will be delivered with the tablet.

Questionnaires will be completed in the same order as the baseline assessment, but preceded by an additional questionnaire based on the theoretical framework of acceptability (TFA), which contains 8 items measuring general acceptability and the 7 distinct components of the framework [27] to assess acceptability of the exercise snacking intervention. Participants will repeat the same tests of physical function as completed in the baseline assessment (including the SPPB previously completed in the screening), under the same conditions as previously.

To complete the physical function tests remotely participants must be accompanied at all times by someone else (e.g. carer or another member of the household). Researchers will instruct the participant on where to place the tablet and chair for the SPPB chair test and STS-60 for a view that allows the test to be carried out as in the baseline assessment. For the balance measures of the SPPB and static standing balance measures, the participant will be reminded that they can position a stable item nearby in case they feel at risk of losing balance. The 2.4 m walk element of the SPPB and the TUG will be omitted in cases where the follow-up testing is completed remotely.

Qualitative assessment of experience of the protocols: Following the intervention participants will be invited to take part in an interview to provide qualitative feedback on their experience of the intervention. Interviews will take place in person or via video calling accordingly, will be digitally recorded, transcribed verbatim and anonymized on completion. The interview schedule will cover; (i) participants' perceptions of the impact of exercise snacking on mood, appetite, vitality, sleep, and other participant-generated concerns, (ii) adherence to the study protocol, i.e., if and how participants adapted the prescribed regimes, and factors they suggest would make the protocol easier to adopt, and (iii) the perceived barriers and facilitators, and costs and benefits of exercise-snacking. Transcripts will be analysed systematically using framework analysis to highlight key themes within and across participants, and the results used to facilitate participant input into the feasibility analysis and protocol amendments.

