semi-tandem stance, full-tandem stance, and single leg standing, with each leg tested in the single leg balance test. The aim of each test is to maintain balance for as long as possible, up to 60 seconds. Each configuration of feet position will be tested twice, with the highest score of the two taken. The first point in time at which either feet or arms are moved substantially (i.e. loss of balance has occurred) will conclude that attempt. The researcher will stand close to the participant to provide physical support if the participant appears to be losing balance, and it will be explained to the participant that they should move from the given stance being tested to prevent falling if necessary

As a measure of functional mobility, participants will be asked to complete a timed-up-and-go test (TUG), in which participants rise from a chair, walk 3 meters, turn around, walk back to the chair, and return to a seated position [25]. This test will also be completed twice, with the fastest time taken.

To assess habitual physical activity levels during the first week of the intervention, participants will then be instructed in the use of, and given a wearable physical activity monitor (ActivPAL). They will be asked to wear the ActivPAL for seven consecutive 24-hour days, and will be provided with a pre-paid and addressed envelope in which to return the device. The ActivPAL provides data on sit-to-stand transitions, and thus will also act as an intervention compliance assessment tool.

Participants will be given an exercise snacking logbook containing full written instructions on how to complete a bout of exercise snacking, and also be given verbal instruction and opportunity to ask questions on its use. The logbook includes space in which to record notes about each exercise snack that may be useful to the researcher or the participant. With the logbook for reference, the participant will perform a bout of exercise snacking as a familiarisation before leaving. The 28-day intervention period will begin the day after the screening and baseline assessment takes place.

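### Remote follow-up keeps the static balance stances but replaces the researcher's close physical support with a companion who has no stated support role and an optional stable item

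*Combined protocol and SAP*

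**What the plan says.** **In person (Section 4.4.3).** The static stances are semi-tandem, full-tandem and single-leg on each side, held for as long as possible up to 60 seconds. "Each configuration of feet position will be tested twice", and the better score counts. An attempt ends at the first substantial movement of feet or arms ("i.e. loss of balance has occurred) will conclude that attempt"). There are two safeguards. "The researcher will stand close to the participant to provide physical support if the participant appears to be losing balance", and participants are told that "they should move from the given stance being tested to prevent falling if necessary".

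**Follow-up (Section 4.4.4).** "The follow-up assessment is planned to take place at the RICE Centre". Video is the fallback if the participant cannot attend, for instance because of lockdown or self-isolation. The tests are to be repeated "under the same conditions as previously". For remote testing, "participants must be accompanied at all times by someone else", a carer or household member being the example given. For the SPPB balance element and the static stances, "the participant will be reminded that they can position a stable item nearby in case they feel at risk of losing balance". Only the SPPB walk and the TUG are dropped.

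**Analysis (Data Analyses).** SPPB and the standing balance scores are secondary outcomes, compared before and after by t-test. No rule covers an SPPB taken without its walk element.

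**The concern.** The cohort is chosen for impaired strength and balance: Section 4.4.2 caps the SPPB at eight out of twelve for that reason. Participants are memory-clinic patients with MMSE scores down to 20. In the remote version, whether anything solid is within reach depends on what the participant chooses to set up.

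The static tests ask for the stance to be held as long as possible. Unless the participant lasts 60 seconds, the attempt ends when balance goes. A researcher on video can see this and stop the test but cannot steady anyone. The requirement to repeat the tests under unchanged conditions therefore cannot be met for this safeguard. What is at stake is avoidable exposure at home, chiefly in single-leg stance, for the sake of secondary data.

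**Working it through.** The plan gives no figure on this point, so the check compares texts and then counts.

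**1. Safeguards side by side, static stances**

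- Physical support: in person, the researcher stands close. Remotely, nobody is assigned to it.
- Companion: not needed for support in person. Remotely, presence is compulsory, but no position, task, capability or briefing is stated.
- Stable item: not mentioned in person. Remotely, it is optional.
- Observation: direct in person, by video remotely. Section 6 has researchers ready to end a session in general terms.
- Step-out instruction: given in person. It is not repeated in the remote text, but plausibly carried over by the same-conditions rule.

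**2. Does any other section restore support?**

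- Section 4.5 (Exercise snacking intervention), Section 5.1 and Section 6 give a companion role for exercise bouts only, and the role is to summon help.
- Section 4.4.2 excludes people who lose balance doing the exercises. Those are sit-to-stand, marching with an optional chair hold, and three seated movements. None is a single-leg stance.
- Section 6 acknowledges a falls risk from exercising at home but does not discuss balance testing at home.

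No section restores physical support.

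**3. Exposure per remote visit** (inputs from Section 4.4.3)

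- Configurations: semi-tandem + full-tandem + left leg + right leg = 4.
- Attempts: 4 × 2 = 8.
- Maximum time: 8 × 60 s = 480 s.
- On one leg: 2 legs × 2 attempts = 4 attempts, at most 4 × 60 s = 240 s.
- With k remote visits: 8k attempts. The documents do not give k. Among the 20 completers planned in Section 4.3 it can be anything from 0 to 20, so the total runs from 0 to 160 attempts.

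The SPPB balance element comes on top of this.

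**4. SPPB total (separate and minor)**

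Section 4.4.2 bars a zero on any SPPB element, so every participant has some walk score at baseline. Setting a remote balance-plus-chair sum against the baseline total would remove those points mechanically and look like decline. If the remote total is set to missing, n = 20 − k pairs remain. The 95% CI half-width for the mean change, in SDs of the change, is t(0.975, n − 1)/√n:

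- k = 0, n = 20: 2.093/4.472 = 0.468
- k = 1, n = 19: 2.101/4.359 = 0.482
- k = 2, n = 18: 2.110/4.243 = 0.497
- k = 5, n = 15: 2.145/3.873 = 0.554
- k = 10, n = 10: 2.262/3.162 = 0.715
- k = 15, n = 5: 2.776/2.236 = 1.242
- k = 19 or 20: fewer than two pairs, so no interval

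The loss is slight if one or two people self-isolate and large if a lockdown catches half the cohort.

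**The case against.** The sponsor plainly thought about remote safety. A companion is compulsory, the stable item is raised specifically for the balance measures, and the two walking tests are dropped. Section 4.4.4 cites earlier video follow-up in shielding older adults. Every remote participant has already done these static tests in person with a researcher close by. An attempt stops at the first substantial movement, which is not a fall. Where the companion stands could be settled on the call, and nothing stops that person from standing close. Making a lay companion a spotter could do harm: they may be unable to hold the participant and could be hurt trying.

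Most of this stands, and it limits both the weight of the point and the remedy. It does not answer the optional item, which is a stated rule and not a missing detail. The cited precedent does not settle safety here either, since the Overview describes experience to date as in healthy older adults.

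Four stronger readings are tempting, and the documents support none of them:

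- *Remote testing is left without protection.* It is not; several safeguards remain.
- *The SPPB balance element also loses documented support.* The close-support sentence is written for the static stances. Section 4.4.2 has no counterpart for the SPPB, so there is no written support to lose.
- *480 seconds measures risk.* It is a ceiling on test time, and no fall rate is available.
- *Few visits will be remote, so the reach is certainly small.* A lockdown could affect many participants at once.

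**Conclusion.** The point holds for the static stances. Documented physical support in person becomes, remotely, a companion without a stated support role and an item that the participant may or may not place. This weakens the safeguard without removing it. The exposure is 8 attempts (at most 480 s) per remote visit, half of them on one leg, for an unknown number of visits between 0 and 20.

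Remote testing is a contingency, the outcomes are secondary, and the primary outcome of acceptability is untouched. It is a change worth considering, not a fault that threatens the study. The conclusion assumes that the step-out instruction carries over to the call and that no separate working instruction, unseen here, already deals with support. The SPPB scoring gap is a separate analysis matter; its cost in precision depends on k, and the figures above assume 20 completers.

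**What to change.** In Section 4.4.4, for remote visits:

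1. Require a stable item within reach for every standing-balance test, and confirm it on camera before starting. Include the SPPB balance element as a simple precaution.
2. Repeat the baseline instruction to step out of the stance to avoid falling.
3. End the attempt if the item is touched. This also keeps remote times closer in meaning to in-person ones.
4. If no stable item can be placed, omit the single-leg stance and record why.
5. Ask the companion to stay nearby and watch, without requiring them to act as a physical spotter.

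In Data Analyses, as a separate sentence: treat a remote SPPB total as missing, and never compare a two-element sum with the baseline score out of twelve.

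The cost is a brief check on the call and occasional loss of secondary single-leg data. If m of the k remote visits lack an item, single-leg balance has 20 − m pairs, with half-widths as listed for the same n. The SPPB rule costs whatever k dictates.
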